View: SF - Research Description

Research Description

1. Describe the study hypothesis and/or research questions. Use lay language whenever possible.

The hypothesis of this prospective single bilind randomized trial is that general anesthesia with laryngeal mark airway is non-inferior in length of procedure to endotracheal tube for patients undergoing abiation for atrial fibrillation.

Secondary hypothesis:
The secondary hypothesis is that general anesthesia with LMA is superior or non-inferior to endotracheal tube in duration of fluoroscopy, post procedure side effects, patient satisfaction and recurrence of PAF.

Describe the study's specific aims or goals. Use lay language whenever possible.
 Study goal is to determine if the use of laryngeal mask airways in abiation of atrial fibrillation is non-inferior to endotracheal tube in terms of procedure length.

3. Describe the study's background and significance, including citations, or upload a citation list in document upload. Use lay

language whenever possible.

In recent years it has been shown that catheter abiation of symptomatic atrial fibrillation (PAF) is superior to antiarmythmic drug therapy with regards to effectiveness and clinical outcomes. 1 Atrial fibrillation is the most common cardiac arrhythmia, with high rates of concomitant heart failure, stroke and mortality.2,3 During an abiation procedure, a patient can be managed with intravenous sedation or General Anesthesia. Within this setting, General anesthesia is associated with improved procedure time and cure rate compared to

Airway management during GA can be achieved through a LMA or an ETT. The use of LMA compared to ETT has been shown in different surgical populations to decrease procedure and recovery time, improve hemodynamic stability and reduce anesthetic requirements.5,6,7 it has also shown to decrease airway complications, and postoperative nausea/vomiting which are important factors that affect overall patient satisfaction.8,9,10,11,12

Although general anesthesia in electrophysiology procedures is associated with a higher cure rate, there have been reports of increased airway trauma.13 Additionally, it is believed that voiatile anesthetics may be associated with increased ventricular action potential duration as well as prolonged QT interval.14,15 The increased usage of opioids during general anesthesia is also thought to interfere with electrophysiology studies by affecting vagal tone.16

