At VCU Health system, Anesthesiologists have been successfully using LMA (General Anesthesia) for ablation in PAF in eligible patients for over five years. The investigators are proposing a randomized, single blind study to evaluate the use of LMA versus ETT in this patient population. A concurrent retrospective study will be conducted to evaluate the last two years data of outcomes in this patient population at VCU. The investigators wish to do a prospective study to reduce bias, as the patients who have greater comorbidities are more likely to have ETT for an esthesia, and we believe this will skew the retrospective data when it is collected. The LMA used at VCU Health are LMA Supreme (Teleflex Medicals, Ireland). The study is designed as a non-inferiority study with a primary outcome of procedure length.

Secondary outcomes will include flouroscopy duration, total anesthesia time, total intra- and post- procedure opioids and ionotropes/pressors/chronotropes, patient satisfaction, PAF recurrence.

Briefly describe the study design, including all interventions or interactions with research participants and access to identifiable data. Use lay language whenever possible.

This will be a prospective, randomized single blind study comparing the use of general anesthesia with endotracheal tube versus laryngeal mask airway in patients undergoing abiation for paroxysmal atrial fibrillation. Patients will be consented the morning of the procedure and will be conducted only by study personnel. All patient identifiers will be stored in a separate, password protected document from data set. Patients will be randomized, data collected and stored in the secure REDCAP database. REDCap database randomization software will be used to randomize patients into one of the two study groups. Patients will be randomized after they sign informed consent the morning of the procedure. Randomization will be done by study personnel using REDCap and verbally conveyed to anesthesia provider that morning of procedure. The minimum necessary study personnel will have access to patient identifiers.

Power analysis: Estimated mean procedure time 3 hours, range 1.5-4.5 hours, standard deviation 0.9, n = 82 to detect 0.5 hour margin of non-inferiority between the two groups. Including 5% drop-outs, final n=87. Goal enrollment 44 patients per group.

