		ocedure pressor/lonotrope/chronotrope requirements: total measured amounts of all pressors/lonotropes and chronotropes stered intraoperatively
	Electro proced	ophysiology Parameters: size of left abrium (mm), left ventricular ejection fraction; duration of paroxysmal abrial fibrillation prior to ure
		trauma: Any noted trauma in the anesthesia or post-procedure notes, including damage to lips/leeth, laryngospasm, need for ation post procedure
	Post-p	rocedure nausea: Measured by number of doses of antiemetics given in the post-procedure time period.
	Post-p	rocedure emesis: Measured by number of times patient has emesis during post-procedure time period.
	proced	ibriliation recurrence: defined as recurrence of paroxysmal atrial fibriliation recurring at any time after 6 weeks past the day of lure. As standard of care these patients are followed up with Holter monitoring for a period of 6 months. Holter monitoring will be or 48 hour time periods immediately post-procedure, 2 weeks, 6 weeks, 4 months and 6 months post procedure as is standard of
	Aspira	tion events: aspiration events as noted in the anesthesia, PACU and post procedure notes would be documented.
		t Satisfaction: patients will be given an survey by study personnel prior to discharge from the hospital; survey will be conducted in by study personnel
	Cost A	nalysis: an analysis of cost to patient as well as overall hospital costs will be conducted
2	Informa	ribe the source(s) of the protected health information: ation will be collected both by reviewing data from the medical record of VCU Health, Cemer as well as by in person surveys cled prior to hospital discharge.
3.	PHI co	ain how the PHI collected or used in this research is the minimum necessary to accomplish this research: illected is minimum necessary to determine our primary and secondary outcomes in determining if the use of LMA is non-inferior to r abilation for atrial fibriliation.
4	. * Selec	ct all pathways this research will employ to use or access PHI:
		- Marine a Robert
		e-Identified Data
	u	mited Data Set
	_ W	laiver of Authorization
	₽ P	artial Walver of Authorization
	₹ \$	igned Authorization Combined with Consent Form
	S	gned Authorization as Stand-Alone Form

De-Identified Data	
Limited Data Set	
Waiver of Authorization	
✓ Partial Waiver of Authorization	
Signed Authorization as Stand-Alone Form	

View: SF - Partial Walver of Authorization

Partial Waiver of Authorization

ID: HM20007902

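### The satisfaction survey is run in person by the same broad staff role that randomises patients, with no requirement that the person running it be unaware of the arm

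*Combined protocol and SAP*

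**What the plan says.** **The survey.** SF - HIPAA, item 1, states that "patients will be given an survey by study personnel prior to discharge from the hospital" and adds that the "survey will be conducted in by study personnel". A word seems to be missing from that second clause in the text as supplied. Item 2, on data sources, fills the gap: information comes from the medical record "as well as by in person surveys".

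**The allocation.** The study design answer in SF - Research Description says: "Randomization will be done by study personnel using REDCap and verbally conveyed to anesthesia provider that morning of procedure".

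**Blinding.** The same answer opens: "This will be a prospective, randomized single blind study comparing the use of general anesthesia with endotracheal tube versus laryngeal mask airway". It does not say who is blinded, and no blinded outcome assessor is described anywhere.

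**The status of the outcome.** The list of secondary outcomes ends with "patient satisfaction, PAF recurrence". The secondary hypothesis is that "LMA is superior or non-inferior to endotracheal tube in duration of fluoroscopy, post procedure side effects, patient satisfaction and recurrence of PAF". In SF - Risks, Discomforts, Potential Harms and Benefits, item 12, better satisfaction is part of the stated scientific benefit.

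**The concern.** Satisfaction is the patient's own judgement, so it can be moved by tone, prompting or the way an answer is written down. Procedure, fluoroscopy and anesthesia times are taken from records in minutes and are far less exposed to this. The team collecting the rating is also the team whose secondary hypothesis favours LMA or parity, and at least some of its members know each patient's arm because they carried out the randomisation.

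Two routes to bias follow. A person who knows the arm may lead the answers. If the patient is the blinded party, which seems likely but is not stated, the encounter may also reveal the arm before the rating is given. The plan has no safeguard against either. Satisfaction as listed in SF - HIPAA is collected by one survey before discharge, so a bias introduced then cannot be put right in the analysis.

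**Working it through.** **1. Who does what**

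| Task | Who | Place in the plan |
|---|---|---|
| Randomise in REDCap and tell the anesthesia provider | Study personnel | SF - Research Description, study design |
| Give and conduct the survey in person | Study personnel | SF - HIPAA, items 1 and 2 |
| Blinded party | Not named | SF - Research Description, study design |
| Separation of the two tasks, or blinding of the survey administrator | Not stated | None found |

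The conclusion rests on this table. The same broad role holds both tasks, and no text keeps knowledge of the arm away from the survey.

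**2. The plan's own figure (context only)**

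The only computed figure is for procedure length: "standard deviation 0.9, n = 82 to detect 0.5 hour margin of non-inferiority between the two groups". Alpha, sidedness and power are not given. Assuming a one-sided alpha of 0.05, 80% power and no true difference:

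n per arm = 2 × (1.645 + 0.842)² × 0.9² / 0.5² = 2 × 6.185 × 3.24 ≈ 40.1, rounded up to 41, so 82 in total.

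This matches the plan. With 5% drop-out, 82 / 0.95 = 86.3, rounded up to 87, and the enrolment goal is 44 per group. The range of 41 to 44 per arm used below comes from here. Nothing in this point changes these numbers.

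**3. What a shift would do (illustration only)**

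Assumptions that are not in the documents: satisfaction is compared by a two-sided 5% test of means, there is no true difference, and the way the survey is run shifts one arm relative to the other by s standard deviations.

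Rejection probability = 1 − Φ(1.96 − s√(n/2)) + Φ(−1.96 − s√(n/2))

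With n = 41, √(n/2) = √20.5 = 4.528. With n = 44, √(n/2) = √22 = 4.690.

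| Assumed shift s | n = 41 per arm | n = 44 per arm |
|---|---|---|
| 0 | 5.0% | 5.0% |
| 0.1 SD | 7.4% | 7.6% |
| 0.2 SD | 14.8% | 15.5% |
| 0.3 SD | 27.4% | 29.1% |

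Only a shift that differs between arms counts, since an equal influence on both cancels in the difference. For the non-inferiority half of the hypothesis no such rate can be worked out, because the plan gives no margin for satisfaction.

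**The case against.** Three stronger readings are tempting, and the documents support none of them.

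- **That the person who randomised a patient also surveys that patient.** A shared role is not a shared person. SF - Data Confidentiality and Storage lists the PI, Co-PI, a research assistant and others, and SF - Consent Groups lists five roles for consent. Someone unaware of the arm could run the survey. The plan neither requires nor excludes this, so the gap is an omission and not proof of an unblinded administrator.
- **That an interviewer reads out the questions and records the answers.** Being given a survey is compatible with a form handed over for self-completion. In the checklist before SF - Data Collection Details, the mark appears beside surveys and questionnaires and not beside interviews, although check marks are read imperfectly from this file. The instrument is not in the supplied text. On the other side, a survey conducted by staff suggests more than handing over a form. The mode is open, and self-completion may already be intended.
- **That self-completion would remove the bias.** It stops prompting and recording by staff. It does not stop influence from staff who hand over or collect the form, or the effect of a patient having learned the arm.

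It is also fair to object that the percentages show nothing about this trial. The documents give no scale, SD, scoring rule or test for satisfaction, and the formal hypothesis is not superiority alone. That objection stands, and the case for change does not rest on the percentages. Finally, this is one secondary outcome among many, and it follows in part from the wider gap that the blinded party is never named. That limits the weight of the point but does not answer it.

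**Conclusion.** The point holds in a limited form. The plan has the satisfaction survey run in person by a role that also randomises and conveys the allocation, and it does not require the administrator to be unaware of the arm. A subjective secondary outcome is thereby exposed to a bias that is cheap to reduce. Whether such a bias would occur, and how large it would be, cannot be settled from the documents. The range of about 7% to 29% for assumed shifts of 0.1 to 0.3 SD shows only how sensitive a comparison of this size would be. Procedure length and the sample size are untouched. This is a worthwhile improvement to one secondary outcome, not a threat to the trial's main conclusion.

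**What to change.** State in the plan who is blinded, which satisfaction instrument is used, and how it is completed. Then:

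1. Have the patient complete the survey unaided before discharge, either as a REDCap survey or on paper in a sealed envelope.
2. Do not disclose the allocation to the patient until the survey is returned.
3. If the patient needs help, use a member of the existing team who did not randomise or attend that case.
4. Record whether the helper knew the arm, so that the final report can say how often this occurred.

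The cost is small. REDCap is already in use, and no new patients or additional staff are needed. The downside is slightly more incomplete items than with staff administration. The change should be in place before surveys are collected.

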Study Population 1. Provide the total number of participants you expect to enroll in this study under the VCU IRB: 2. If this is a multi-Center Project, what is the total anticipated number of subjects across all sites: 3. * Provide justification for the sample size: Power analysis: Estimated mean procedure time 3 hours, range 1.5-4.5 hours, standard deviation 0.9, n = 82 to detect 0.5 hour margin of non-inferiority between the two groups. Including 5% drop-outs, final n=87. Goal enrollment 44 patients per group 4. * List the study inclusion criteria: Patients undergoing primary abilation for paroxysmal atrial fibrillation - Able to obtain consent in English language 5. * List the study exclusion criteria: - Patients <18 years old Patients undergoing abiation for arrhythmias other than paroxysmai atrial fibrillation American Society of Anesthesiologist physical status of 4 or greater Patients undergoing repeat abiation - Pregnancy Prisoners - Patients unable to give their own consent - Patients having trans esophageal echo on the same day - Patients unable to give consent in English language - Patients will also be excluded if the attending anesthesiologist determines that they would not be suitable candidates for intubation with either method (ETT tube or LMA mask). - Patients with severed gastroesophageal reflux disease - Patients with high risk of aspiration 6. * Check all participant groups that are likely to be involved in this study. If it is possible that a regulated vulnerable population (children, pregnant women, prisoners) COULD BE involved in the study, be sure to check them: Healthy Volunteers Children Emandpated Minors Pregnant Women Fetuses, Neonates, Fetal Material or In-Vitro Fertilization Decisionally Impaired Adults When cancer is integral to the research - cancer Patients, Family Members, Healthcare Providers or Prevention VCU Health System Patients ■ Non-VCU Patients ■ VCU/VCUHS Employees Individuals with Limited English Proficiency Active Military Personnel When researching in a K-12 environment - populations Within School Districts or Other Learning Environments 7. If you are either targeting, or excluding, a particular segment of the population / community, provide a description of the group/organization/community and provide a rationale: Patients who are unable to consent in english language are being excluded as the investigators feel that it would be difficult to uniformly obtain informed consent and collect dta in this patint population. 8. * Select the age range(s) of the participants who may be involved in this study: < 1 Year
 1 - 6 Years 7 - 12 Years 13 - 17 Years √ 18 - 20 Years 21 - 65 Years > 65 Years View: SF - Potential Subject Identification and Recruitment ID: HM20007902 Potential Subject Identification and Recruitment 1. * Choose all recruitment methods that may be used:

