
E-mail Campaign
Phone Solicitation
Flyers, Letters or Newspaper/TV/Radio Ads
Website

₹ [Direct Contact
	Psychology Research
	Participant Pool (SONA)
_ \	/CU TelegRAM announcement
	Nord of Mouth
	Other
If Ot	her, please describe:
* Sele	ect the methods used to obtain names and contact information for potential subjects:
	Pre-Existing Relationship with Participants
7	Selected from Pre-Existing VCU Records
	Selected from Pre-Existing Non-VCU Records
	Selected from Publicly Available Records
	Referred by Health Care Provider or Other Health Professional
_	Recruited from Database or Registry
_	dentified through Community Based Organization (Schools, Church Groups, etc.)
_	
_	Self Referred (Flyer/Ad)
	Other
If Oth	er, please describe:
	cribe specific details for identifying and recruiting participants, including but not limited to: cific locations where recruitment materials will be displayed
- How	or contact information is obtained for any direct contact with potential participants owill approach and/or respond to potential participants:
No re	crultment materials will be displayed. Direct contact will be done in the pre-procedure area of electrophysiology at VCU Health.
	r personnel as listed will approach potential participants who have been determined to be eligible for participation in study. Contact nation will be from electrophysiology schedule and pre-screening of potential study participants.
ablati	nt screening will be done by evaluating the posted schedule for electrohysiology for each day and potential patients undergoing on for atrial fibriliation will be identified. These charts will then be evaluated to determine if they qualify given the studies strict
	ion/exclusion criteria.
	ribe any special recruitment procedures for vulnerable populations:
	ad all recruitment materials including ads, flyers, scripts, letters, email invitations, TelegRAM announcements, and eard reminders:
done	ore potential participants consent to the study, will screening questions be asked or will any screening procedures/tests be that would not otherwise be done as standard of care:
	, will identifiable information about individuals be recorded during screening:
ON	
OY	lo .
ON	lo .
⊝ Y ⊝ N 2000	7902 View: SF - Privacy
2000 ac	View: SF - Privacy

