- If the disclosure of any of the information obtained during the study would place the individual at risk for harm (legal, reputation, emotional etc.) and the information will be recorded so that the individual could be identified, explain the protections that will be put in place to decrease the risk of disclosure:
- 4. * The Code of Virginia requires that most medical personnel and all employees of institutions of higher education report suspected child/elder abuse or neglect. Is it likely investigators could discover information that would require mandatory reporting by the investigators or staff:
 - Yes
 - No
- 5. Is it likely investigators could discover a participant's previously unknown condition (eg disease, suicidal thoughts, wrong paternity) or if a participant is engaging in illegal activities:
 - Yes
 - No
- 6. If yes, explain how and when such a discovery will be handled:
- 7. Describe any potential risks or harms to a community or a specific population based on study findings: There is minimal to no risk or harms to a community or specific population based on study findings.
- Pescribe criteria for withdrawing an individual participant from the study; such as safety or toxicity concerns, emotional distress, inability to comply with the protocol, etc.:

Participants will be withdrawn from the study if they are converted from their initial randomization. They will also be withdrawn if they request to be removed from study. Patients who do not complete all the post discharge holter monitor evaluations will be kept in the study, and the missed data fields will not be evaluated for that specific patients

- Summarize any pre-specified criteria for stopping or changing the study protocol due to safety concerns:
 No specified criteria for stopping or changing study protocol for safety concerns.
- 10. Where appropriate, discuss provisions for ensuring necessary medical, professional, or psychological intervention in the event of adverse events to the subjects:
- 11. Describe any potential for direct benefits to participants in this study: Participants in this study have potential for benefits of possibly fewer side effects, while also having a similar outcome with regards to

12. * Describe the scientific benefit or importance of the knowledge to be gained: The scientific benefit of knowing if the use of LMA is associated with similar (non-inferior) outcome in term of procedure length and

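### The airway-suitability exclusion, read literally, admits patients suited to only one device, and the withdrawal-on-conversion rule can then drop them according to arm

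*Combined protocol and SAP*

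**What the plan says.** **Criterion.** Study Population, item 5, lists among the exclusions patients who will be "excluded if the attending anesthesiologist determines that they would not be suitable candidates for intubation with either method (ETT tube or LMA mask"). It gives no basis for the judgement, no time for it and no place to record it.

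**Screening.** Potential Subject Identification and Recruitment describes study personnel working from the posted procedure schedule: "These charts will then be evaluated to determine if they qualify given the studies strict" criteria. The same section says personnel "will approach potential participants who have been determined to be eligible for participation in study". Partial Waiver of Authorization also describes a brief chart review for eligibility before consent.

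**Allocation.** Research Description, item 4: "Patients will be randomized after they sign informed consent the morning of the procedure". The result is then "verbally conveyed to anesthesia provider that morning of procedure". Consent Groups puts the approach to the patient about 30 minutes to 1 hour before the procedure starts.

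**Removal after allocation.** Risks, Discomforts, Potential Harms and Benefits, in the answer on withdrawing participants: "Participants will be withdrawn from the study if they are converted from their initial randomization". No intention-to-treat or per-protocol set is defined.

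**Usual practice.** Research Description, item 3, explains the choice of a prospective trial by noting that "patients who have greater comorbidities are more likely to have ETT".

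**The concern.** The criterion turns on the word *either*. As the sentence stands, a patient must be unsuited to both devices to be excluded. It could also be meant to exclude anyone unsuited to at least one, but nothing settles this. Under the literal reading, a patient with only one acceptable device enters the trial with an even chance of being assigned the other.

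Entry alone would not distort the comparison. The difficulty is the conversion rule. A one-device patient who draws the suitable device stays, and the same kind of patient who draws the other device is converted and withdrawn. The two arms then lose different kinds of patient, and the people analysed are no longer the groups that randomisation formed. The trial was designed to avoid choice of airway by comorbidity, and this route lets part of it back in.

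The criterion also needs the attending's own determination, while the screening described is a chart review by study personnel. No readable passage puts the attending's judgement before the anesthesia provider hears the allocation. An explicit lock on this one subjective criterion is missing.

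**Working it through.** **1. The plan's own figure.** Inputs from Research Description, item 4: SD 0.9 h, margin 0.5 h, n = 82 in total, 5% drop-out, 87 in total, 44 per group. Alpha and power are not stated. With a true difference of 0, one-sided 5% and 80% power:

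n per arm = 2 × (1.645 + 0.842)² × 0.9² / 0.5² ≈ 40.1, rounded up to 41, so 82 in total.

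82 / 0.95 = 86.3, rounded up to 87. The stated size reproduces. One-sided 2.5% would give 102 (80% power) or 138 (90%), and one-sided 5% with 90% power would give 112. A one-sided 5% level is therefore the natural baseline below, but it is inferred.

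**2. Who is lost, by type of patient (literal reading).**

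| Attending's view | Excluded at entry? | Assigned LMA | Assigned ETT |
|---|---|---|---|
| Both devices suitable | No | Kept | Kept |
| Only ETT suitable | No | Converted, withdrawn | Kept |
| Only LMA suitable | No | Kept | Converted, withdrawn |
| Neither suitable | Yes | – | – |

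If the criterion required both devices to be suitable, only the first row would be randomised. The middle rows would not arise, except through conversions nobody foresaw.

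**3. Size, as an illustration.** The documents give none of these inputs; all are assumed.
- Share of the LMA arm removed: p = 5% to 10%, or 2.2 to 4.4 of 44 patients. None is removed from the ETT arm.
- Those removed would have had procedures d = 0.45 to 0.9 h (0.5 to 1 SD) above the full-arm mean.

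Shift in the retained LMA mean = p × d / (1 − p):
- low: 0.05 × 0.45 / 0.95 = 0.024 h, 5% of the margin
- high: 0.10 × 0.9 / 0.90 = 0.10 h, 20% of the margin

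Standard error of the difference at 44 per arm = 0.9 × √(2/44) = 0.192 h.

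Type I error at a true difference of 0.5 h = Φ(−z + shift / 0.192):

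| Nominal one-sided level | Low case | High case |
|---|---|---|
| 5% (z = 1.645) | 6.4% | 13.1% |
| 2.5% (z = 1.96) | 3.3% | 7.5% |

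Two checks on the high case at 5%. Allowing for the smaller LMA arm (39.6 patients) raises the standard error to 0.197 h and gives 12.8%. Measuring d against the retained patients makes the shift p × d = 0.09 h and gives about 12%.

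**4. The other direction.** If longer procedures are lost from the ETT arm instead, the shift goes against LMA. A shift of 0.10 h cuts power at a true difference of 0 from 83% to 67% (one-sided 5%, 44 per arm).

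**The case against.** The strongest reply is that the plan already puts eligibility first. Patients are approached only once found eligible, consent follows, and randomisation follows consent. The disputed item is an entry exclusion, and nothing permits its use after allocation. Neither meaning of *either* depends on the arm, so using it selectively by arm would be a misapplication. All of this stands. A reader might infer that the plan lets the attending exclude patients knowing their arm; the documents do not support that. They leave one criterion without a recorded time, which is a smaller fault. Some of the text on screening and on informing staff is also unreadable, so the absence can be stated only for what can be read.

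It is also fair that the harm to the comparison runs mainly through the conversion rule, and that applying the criterion before allocation would by itself change only who enrols. The eligibility wording still matters, because literal use of it before allocation supplies the one-device patients on whom the conversion rule then acts.

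A reader might further infer that the result is biased toward non-inferiority. The remark that sicker patients tend to receive ETT makes losses from the LMA arm plausible. However, it describes past non-randomised practice, and no passage links airway unsuitability or comorbidity to longer procedures. Losses from the ETT arm would push the other way. Separate exclusions for ASA status 4 or above, severe reflux and high aspiration risk already remove part of the group likely to be judged unsuited to LMA. They do not cover every reason for rejecting a device.

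**Conclusion.** The point holds in a limited form. Followed as written, the plan can randomise a patient to a device the attending considers unsuitable and then remove that patient in a way that depends on the arm. Nothing readable requires the suitability judgement to be recorded before the allocation is known.

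The direction of any bias is open. The figures of 0.02–0.10 h and a type I error of about 6–13% (3.3–7.5% at a one-sided 2.5% level) show what would follow if losses fell only on the LMA arm and those patients had longer procedures. They rest on an assumed removal share, an assumed excess duration, no removal from ETT and an inferred significance level. They do not predict what this trial will produce. The stated sample size is not in dispute.

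**What to change.** 1. Reword the exclusion so that a patient is randomised only if the attending judges both the ETT and the LMA suitable. Avoid the word *either*.
2. Have that judgement entered in a required REDCap field, with the randomisation step disabled until it is complete.
3. State that the criterion cannot be invoked once the allocation is known.
4. For analysis, replace withdrawal on conversion: all randomised patients who have the procedure are analysed in their assigned arm, and their procedure time is collected whatever airway was finally used. Withdrawal at the patient's own request is unaffected. Add a supporting analysis that excludes converted patients, and report conversions by arm with reasons.

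These changes concern eligibility recording and analysis. They leave the attending's decisions about the airway during the procedure untouched.

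The cost is a revised criterion, one REDCap field, a revised withdrawal paragraph, a short conversation with the attending before randomisation, and one extra analysis. No change in sample size follows.
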